Estimated sample size of 30 final participants based on our current best knowledge based on prior trials of the pad we have conducted.

Methodology - clearly describe the specific procedures or techniques that will be used to answer the research question and meet the aims.

Participants will be randomly allocated into either the treatment or control group by odd vs even number selection. In the control group, participants will conduct their normal lymphoedema care routine. In the treatment group, the participant's lymphoedematous leg will be treated with the Niagara® Cyclopad for a total of 30 minutes (i.e. 10 minutes each in three locations; lower back, upper leg and lower leg) using the set minimum frequency. There will be 5 cycles of deep breathing before and after the massage pad use. Participants will be asked to rest supine for 15 mins prior to starting each treatment. At the end of their 4-week follow-up period, the participant will be crossed over into the other group.

Measurement points are:

- Screen
- Baseline
- Day 1/2 (phone call)
- Day 4
- 1 week
- 2 weeks
- 3 weeks
- 2 weeks Follow-up
- 4 weeks Follow-up

Please see Table 1 for Schedule of assessments.

Procedure	SCREEN	BASELINE	PHONE CALL (Day 1 or 2)	DAY 4	WEEK 1	WEEK 2	WEEK 3	FOLLOW-UP 1 (2 weeks)	FOLLOW-UP 2 (4 weeks)	
			Treatment or Control Phase						Post-Treatment/Control Phase	
Visit	1	2	3	4	5	6	7	8	9	
Informed Consent	✓									
Eligibility Criteria	✓									
Demographics	✓									
Medical History	✓									
Physical Exam	✓	✓								
Vital Signs	✓	✓		✓	✓	✓	✓	✓	✓	
Height	✓	✓								
Weight	✓	✓		✓	✓	✓	✓	✓	✓	
LYMQOL		✓					✓	✓	✓	
Symptom Scale (10-point Likert)		✓					✓	✓	✓	
Bioimpedance	✓	✓		✓	✓	✓	✓	✓	✓	
Limb Volume	✓	✓		✓	✓	✓	✓	✓	✓	
MoistureMeter D		✓		✓	✓	✓	✓	✓	✓	
Tonometry/Skin FibroMeter		✓		✓	✓	✓	✓	✓	✓	
Concomitant Medications	✓	✓		✓	✓	✓	✓	✓	✓	
Review Participant use of device in-situ			✓							
Review Participant Diary			✓	✓	✓	✓	✓			
Sonography		✓					✓	✓		

crossover to other group

Procedure	BASELINE	PHONE CALL (Day 1 or 2)	DAY 4	WEEK 1	WEEK 2	WEEK 3	FOLLOW-UP 1 (2 weeks)	FOLLOW-UP 2 (4 weeks)	
			Treatment or Control Phase					Post-Treatment/Control Phase	
Visit	10	11	12	13	14	15	16	17	
Informed Consent									
Eligibility Criteria									
Demographics									
Medical History									
Physical Exam	✓								
Vital Signs	✓		✓	✓	✓	✓	✓	✓	
Height	✓								
Weight	✓		✓	✓	✓	✓	✓	✓	
LYMQOL	✓					✓	✓	✓	
Symptom Scale (10-point Likert)	✓					✓	✓	✓	
Bioimpedance	✓		✓	✓	✓	✓	✓	✓	

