How are potential participants identified as suitable for the research?

Advertisement notice attached separately. Participants will be recruited from the local lymphoedema clinics and by word of mouth from those who decided to participate. Advertisement will be placed on relevant notice boards in clinics. All will be provided with the full details (see PICF) if they express verbal interest.

How will participants be recruited into the study?

Potential participants will see advertisement and then on the basis of that decide if they wish to participate. We anticipate some interest by word of mouth and in these cases the potential participant will be provided with the advertisement, followed by the PICF if still interested.

Who is approaching the participants about this research project?

Self-identification through awareness of the ad or Lymphoedema Therapist will notify a potential participant of the study.

When is this occurring?

Clinic – a lymphoedema therapist will notify the potential participant that the trial is available.

Are participants reimbursed for parking, travel or time involved?

- No
 Yes

Please detail what is being reimbursed and the amount:

Participants will be reimbursed \$10 for parking and provided a \$10 gift voucher for a light meal or drink at a local café. Participants will be able to keep the massage pad provided to them during the trial at the end of the study.

Participant commitment -

Participants will have 17 appointments over the full crossover study design (from screening to 4 week follow-up). Two of these visits will be a phone call (Day 1 or 2). Assessments are non-invasive and outlines in the Methodology Section.

Participant follow up –

Participants have clinic appointments at Screening, Week 1, Week 2, Week 3, 2-week Follow-Up and 4-week Follow-Up (for both the treatment and control arm). There will be a phone call on Day 1 or Day 2 to monitor progress and home use of the massage pad.

Ethical considerations

Please describe the risk and burden associated with your research.

This research is of no risk of harm or discomfort and no risk for minor burden or inconvenience. The only foreseeable risk is no greater than discomfort. The massage pad is a TGA-approved medical device, class IIa (ARTG 151788) and the assessments are non-invasive. There is a risk the quality of life questionnaire (LYMQL) may cause distress. Counselling will be provided if required.

How will any risks be managed?

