Matching and sampling strategies: Participants will be randomly allocated into either the treatment or control group by odd vs even number selection. After the 4 week follow-up period, the participants will be crossed over into the other group (treatment or control). In the event a participant does not wish to participate in the second group then either another participant who intends to participate in both will be chosen or a second participant chosen with matching bio data (Age, gender, BMI).
Accounting for potential bias, confounding factors and missing information: Randomisation will help avoid bias. We will also be able to observe if there are conditions such as psoriasis, infection etc on the limbs and exclude participants if not declared in initial responses. Missing information is unlikely due to the short time of the intervention and measurement period. Should it occur due to equipment failure then the participant could be invited to return. Failing this the data set would be excluded from the analysis
Sample size and statistical or power issues –

This study is one following information collected from a prior pilot trial and has informed us a sample size of 30 is adequate. While a statistical outcome is useful, we also will examine what we see as “biological” or “practical” changes. However, given the relative homogeneity of the sample and the fact that we do not intend to undertake or rely on any subgroup analysis the sample size of 30 is adequate. The equipment we use i.e., perometry is able to accurately and detect changes in limb volumes of 50ml in a 5000ml limb section and our Bio-impedance analysis unit can detect fluid changes of 10ml per limb.

How will you measure, manipulate and/or analyse the information collected?

All data will be used in its raw form as generated by the measuring equipment. Analysis initially by excel and followed by analysis using STATA or similar statistical program as appropriate.

Data linkage – what linkages are planned or anticipated?

None

Participants may withdraw from the study by choice, what impact will a participant withdrawing have on the data?

Should they withdraw, they will be replaced by another matched participant completely or for the arm of the trial that they withdrew from. Given the massage pad is available on the market and this is low risk research, we don't anticipate many participants to withdraw.

How will this be responded to?

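### The missing-reading rule can discard usable crossover data, and the undeclared-condition rule may allow exclusion after randomisation

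*Protocol*

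**What the plan says.** All of this is in the Analysis section of the protocol, in the paragraph on bias, confounding and missing information, unless another place is named.

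- **Expectation.** "Missing information is unlikely due to the short time of the intervention and measurement period".
- **Missing readings.** If equipment failure causes a gap, the participant could be invited back. If that does not work, "Failing this the data set would be excluded from the analysis". No other handling of a missing reading is stated. Withdrawals have their own rule, which is replacement by a matched participant.
- **Conditions on the limb.** Staff expect to be able to see conditions such as psoriasis or infection, and may "exclude participants if not declared in initial responses". No visit or time limit is attached.
- **Sample size.** The Recruitment target gives "Estimated sample size of 30 final participants based on our current best knowledge". The Analysis section says a prior pilot "has informed us a sample size of 30 is adequate".
- **Burden.** Under Participant commitment: "Participants will have 17 appointments over the full crossover study design". Two of these are phone calls.

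**The concern.** The two rules raise different problems.

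The first is efficiency. In a crossover each participant supplies data under both conditions. If *data set* means the participant's record, a device fault at one visit removes sound readings from every other visit and from both periods. With 30 participants and no stated allowance for such losses, that could matter.

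The second is bias. The paragraph relies on randomisation to avoid bias, but that protection holds only while randomised participants stay in the analysis. A skin condition or infection that appears on the study leg during the trial happens after randomisation and may be related to the lymphoedema or to the device. The comparator described under Methodology is normal care, staff check pad placement by phone, and the study coordinator collects everything except the ultrasound data. Whoever decides on an exclusion is therefore likely to know the current condition, and no rule for deciding blind to it is stated.

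**Working it through.** **1. The plan's own figure.** The 30 cannot be reproduced. No effect size, SD, alpha, sidedness or power is stated. The only figures offered are instrument limits: perometry can "detect changes in limb volumes of 50ml in a 5000ml limb section", and bioimpedance 10 ml per limb. These are neither a target difference nor an SD.

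**2. How many readings are exposed to the rule.** From Table 1:
- Clinic visits after screening: visits 2 and 4–9 (7), and visits 10 and 12–17 (7), so 14.
- Duration: 3 + 4 + 3 + 4 = 14 weeks.
- Four devices at each visit: 14 × 4 = 56 sessions. Sonography at three visits per period: 6 sessions. Total 62 per participant.

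**3. Participants left complete.** Expected number = 30 × (1 − q)^k, where q is the chance that a session fails and is not recovered, and k is the number of sessions that trigger deletion. The values of q are assumptions, and failures are taken as independent.

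| q | k = 62 (whole record, any device) | k = 14 (one instrument's series) | k = 4 (one instrument, baseline and week 3, both periods) |
|---|---|---|---|
| 0.1% | 28.2 | 29.6 | 29.9 |
| 0.25% | 25.7 | 29.0 | 29.7 |
| 0.5% | 22.0 | 28.0 | 29.4 |
| 1% | 16.1 | 26.1 | 28.8 |

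**4. What that would mean for power.** For illustration only, assume a paired t-test at two-sided 5%. Power is P(T > t(0.975, n − 1)), with T noncentral t on n − 1 degrees of freedom and noncentrality d√n.
- If 30 gives 80% power (d = 0.53): 77% at n = 28, 66% at n = 22, 51% at n = 16.
- If 30 gives 90% power (d = 0.61): 88%, 78% and 63%.

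**5. How far selective exclusion could move the estimate.** As an extreme case, 20,000 simulated samples of 30 within-participant differences were drawn with no true effect, and the worst 1, 2 or 3 were dropped from each. The mean shifts toward benefit by 0.07, 0.13 or 0.19 SD. This assumes that the excluded participants are exactly those with the worst results. It shows how far so few exclusions could move the mean and is not a forecast.

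**6. The undeclared-condition rule against the rest of the protocol.**
- The Exclusion Criteria cover current or recent bacterial infection, wounds and skin breakdown. Psoriasis is not named there, so the Analysis section adds a ground that the eligibility list lacks.
- Table 1 places a physical exam at Screen, at Baseline and again at visit 10, the second-period baseline. The leg is also measured at every clinic visit. A condition can therefore be noticed after allocation, and nothing in the rule stops it being applied then.
- The text does not say at which visit allocation takes place.

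**The case against.** The case for the plan has real weight.

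- **The deletion rule is narrow.** A reader might infer that a participant is dropped whenever any reading is missing. The protocol does not say that: the rule is tied to equipment failure and applies only after a return visit has been considered. A missed visit has no stated rule.
- **The term may be narrow too.** Under Data sets, the data management plan lists data by instrument or source, so losing one instrument's data is a natural reading. The same plan also uses the term for the whole study file, which leaves it ambiguous.
- **Equipment failure is not plausibly related to outcome or condition.** The first rule therefore costs precision. It does not by itself make exclusion depend on outcome.
- **The second rule may concern entry only.** Its wording about initial responses fits a condition that was present at the start and not disclosed, which the exams at Screen and Baseline would show. Outcome-dependent exclusion is possible under the text but not established by it.
- **Thirty is described as a final number, and withdrawals are replaced.** That may soften the loss, but replacement is stated for withdrawals and not for data excluded after a device failure.
- **Seventeen appointments do not contradict a forecast of little missingness.** They only make it look optimistic.

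These points limit the size and certainty of the problem. They do not remove it. Deletion remains the only stated fallback for a reading that cannot be repeated, and the exclusion rule still has no time limit.

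**Conclusion.** The point stands in a limited form. The protocol fixes a deletion rule that can waste valid crossover data, and an exclusion rule that may reach randomised participants. Both are written commitments, so this is more than detail left to a statistical analysis plan.

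The loss of power runs from negligible (about 29 of 30 kept) to large (about 16 of 30) at the same assumed 1% failure rate, according to what *data set* means. It cannot be narrowed from the document: the failure rates are assumed, and the power figures rest on effect sizes chosen so that 30 gives 80% or 90%. The bias from the second rule is a possibility with an illustrative size of 0.07 to 0.19 SD in the extreme case. The inconsistency over psoriasis is plain on the page.

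**What to change.** Replace the deletion sentence with wording such as: *All observed measurements of all randomised participants are analysed, for example in a linear mixed model with treatment, period and sequence and a participant random effect; a missing reading removes only that reading.* If the term *data set* is kept anywhere in the rules, define it.

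State that eligibility exclusions for undeclared conditions are made only before allocation, at Screen or Baseline, and say when allocation occurs. Reconcile the mention of psoriasis with the Exclusion Criteria.

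State that conditions found after allocation are recorded, that the participant's data stay in the main analysis, and that a sensitivity analysis omits them. This concerns the analysis only. Clinical decisions about whether a participant continues are unaffected.

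The cost is a few sentences and slightly more analysis work. No data collection changes, and the model can be fitted in the STATA software that the protocol names.

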What are the research activities this person will be responsible for: Study Coordinator; Ethics submissions, placing advertisements, recruitment, assisting entry of participants into trial, data collection/measurement of parameters in the trial (except those associated with Ultrasound Doppler which will be carried out by a Sonographer), data entry, preparation of data for analysis	
Does this person have a current Good Clinical Practice certificate that you will submit with your application?  Yes /  No - Good Clinical Practice training is required by all listed investigators, as per National Clinical Trials Governance Framework action 1.2 and 1.6	
Contact details: a Health or University email address must be used  I am the contact person for this project	[contact] Email: [contact]

Research Overview

Please provide a brief overview of the study:

Recruit and conduct a single site randomised controlled crossover clinical trial of the impact of 3 weeks home use of **Niagara® Cycloid®** massage pad action on chronic unilateral chronic oedema/lymphoedema of the legs arising as a consequence of treatment for cancer of the bowel, other abdominal structures (including ovaries and prostate) and melanoma. There will be a follow up period at 2 weeks and at 1 month. The massage pad is a TGA-approved medical device, class IIa (ARTG 151788).

Background and literature review

Correctly and externally applied vibration is widely regarded as having a potential for bringing about improvements in a range of health disorders and conditions as well as when there are undiagnosed or un-recognised pathologies. Human studies have shown that cycloid vibration therapy (CVT) applied externally to the skin can increase venous and arterial blood flow and the movement of interstitial fluid in people with lymphoedema (swelling caused by abnormal accumulation of lymph fluid). This increased local area blood flow may assist in the reduction of lymphoedema, musculoskeletal pain and improve joint mobility. In turn, improving quality of life and general wellbeing.

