Participant is free to withdraw from the study if they find the treatment discomforting.

Benefits – please identify and explain the expected outcomes and benefits of the study

The outcome will be an improved understanding of the impact of CVT on the blood flow into and out of lymphoedematous legs and of its impact on overall leg and fluid volumes. As well as perceived impact of the participant on symptoms and quality of life and use of the device.

Does a dependant or unequal relationship exist between the participant and the researcher?

- Yes -
How will the dependant / unequal relationship be managed?
 No

Conflicts of interest: Please refer to the National Statement chapter 5.4, and your institutional policy for guidance.

- Yes / No

Please provide details of the conflict of interest and how it will be managed:

Data management plan

Which listed investigators will collect the study data / information?

SC will collect all data and enter into an Excel spreadsheet (located on Flinders University password-protected computer drive). Sonographer will collect ultrasound data and SC will enter this into the spreadsheet.

What type of data will be used?

- Data that has never been labelled with individual identifiers or from which identifiers have been permanently removed, and by means of which no specific individual can be identified.
- Identifiable - data that contains an identifier or combination of identifiers i.e. name, date of birth, image, address, URN
- Data in which identifiers have been removed and replaced by a code, but it remains possible to re-identify a specific individual by, for example, using the code or linking different data sets.

If the data being used has the potential to identify a patient, please justify and describe how accidental re-identification will be avoided?

Any identifying codes will be removed and replaced by numbers only.

If the participant's medical records are being accessed - please state where the information is being collected

N/A

Data sets -

Ultrasound doppler – flow rates, flow volumes from major artery and veins on both legs, as per the data output from the Doppler unit. This is then transcribed into an excel data sheet.

Perometry - the total volume and circumferences of both limbs are noted from the perometry program and transcribed into the excel data sheet.

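### A withdrawn arm may be filled by a different, matched person, so that arm is not randomised and the treatment-control pair spans two people

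*Protocol*

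**What the plan says.** The Research Overview describes a "single site randomised controlled crossover clinical trial". Allocation is described under Methodology and again under Analysis: "Participants will be randomly allocated into either the treatment or control group by odd vs even number selection". Each person crosses to the other group after the 4-week follow-up. Under Analysis, the protocol relies on randomisation to avoid bias.

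Replacement is set out twice in the Analysis section.

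- Under matching and sampling strategies, a person who does not wish to enter the second group is replaced in one of two ways. Either another participant who will do both groups is chosen, or "a second participant chosen with matching bio data (Age, gender, BMI").
- In the answer on the impact of withdrawal: "Should they withdraw, they will be replaced by another matched participant completely or for the arm of the trial that they withdrew from".

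The protocol does not say whether replacements are randomised, how a withdrawn person's completed data are used, or how a pair made of two people is analysed. It expects few withdrawals but gives no number.

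The recruitment target is "Estimated sample size of 30 final participants". The power paragraph rests this on "information collected from a prior pilot trial and has informed us a sample size of 30 is adequate" and adds "given the relative homogeneity of the sample and the fact that we do not intend to undertake or rely on any subgroup analysis".

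**The concern.** The replacement rule has two routes. The one-arm route undoes what a randomised crossover provides.

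- **Allocation.** The vacant arm is known before the replacement is chosen, so chance does not decide that person's treatment. The control is normal care, so nothing masks which arm is being filled.
- **Pairing.** The treatment-control contrast is then between two people. Matching covers age, gender and BMI. It does not cover baseline limb volume, duration of swelling (eligible range 1.5 to 10 years), nodes removed or radiotherapy.
- **Sequence and period.** A person brought in only for the second period has had no first period, so neither term is defined for that composite pair.
- **Selection.** The section on managing risks says: "Participant is free to withdraw from the study if they find the treatment discomforting". If people leave for that reason, or for lack of benefit, filling their place with someone else selects for people who tolerate the pad or do well on it.

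This rule governs who enters the trial and in which arm, and it applies from the first withdrawal. An analysis plan written later cannot turn a chosen replacement into a randomised one.

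**Working it through.** **The protocol's own figure.** The 30 cannot be reproduced. No alpha, power, effect size, standard deviation, within-person correlation or dropout rate is given. What follows is an illustration on stated assumptions.

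**Inputs**

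- From the protocol: 30 final participants.
- Assumed: two-sided alpha 0.05, and 80% power when all 30 pairs are true within-person pairs.
- Assumed: *m* = 3 pairs made of two people, analysed as ordinary pairs.
- Assumed: correlation ρₘ = 0.3 between matched people, and within-person correlation ρ from 0.5 to 0.95.

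**Formula.** The variance of the mean of 30 differences, *m* of them between two people, is

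[(30 − m)·2(1 − ρ) + m·2(1 − ρₘ)]·SD² / 30².

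Dividing by the value for 30 true pairs, 2(1 − ρ)·SD²/30, gives the variance ratio

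R = [(30 − m)(1 − ρ) + m(1 − ρₘ)] / [30(1 − ρ)].

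For m = 3 and ρₘ = 0.3 this is R = 0.9 + 0.07/(1 − ρ). The equivalent number of true pairs is 30/R. By normal approximation, power is Φ(2.80/√R − 1.96), where 2.80 = 1.96 + 0.84.

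| ρ | R | True-pair equivalent | Power |
|---|---|---|---|
| 0.5 | 1.04 | 28.8 | 78% |
| 0.7 | 1.13 | 26.5 | 75% |
| 0.8 | 1.25 | 24.0 | 71% |
| 0.9 | 1.60 | 18.8 | 60% |
| 0.95 | 2.30 | 13.0 | 46% |

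**Sensitivity**

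- Number of two-person pairs: at ρ = 0.8, one gives 77% power and five give 65%. At ρ = 0.95, five give 35%.
- If matching leaves no correlation (ρₘ = 0), three two-person pairs give 71% at ρ = 0.7 and 53% at ρ = 0.9.

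**Comparison with no replacement.** Analysing 27 complete pairs gives Φ(2.80·√(27/30) − 1.96) = 76%, whatever ρ is. Setting 0.9 + 0.07/(1 − ρ) equal to 30/27 = 1.11 gives ρ of about 0.67. Above that value, one-arm replacement in an ordinary paired analysis is less precise than leaving the three places empty.

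**Bias.** Its size cannot be derived from the protocol. As a scale only, suppose three replacements differ in raw leg volume from those they replace by an average *g*, always in the direction that moves the contrast the same way. The mean difference shifts by 3g/30. For g = 250, 500 and 1000 ml (assumed) the shift is 25, 50 and 100 ml. The power paragraph says perometry can detect 50 ml in a 5000 ml section. This example applies to unadjusted volumes.

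**The case against.** Several points on the other side are sound.

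- **The large power losses need a high correlation on unadjusted levels.** Table 1 repeats baseline at the start of each period (visits 2 and 10). If the contrast is change from each period's own baseline, most stable difference between people cancels even in a two-person pair. The relevant correlation is then between two changes, and the loss is probably small. The statement that data are used in raw form does not settle which contrast is analysed, and an analysis plan not available here may. This stands, so the 46% is the end of a range and not an expected value. The same limit applies to the raw-volume bias example.
- **Full replacement is different.** A new person who does both periods keeps the within-person comparison, and the text does not exclude randomising that person. This stands. What remains for that route is the unstated allocation and the selection of completers.
- **Few withdrawals are expected.** With none, the rule does nothing. This limits the size of the problem, but even one one-arm replacement is a non-randomised arm.

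A reader might infer more than the protocol supports on three points.

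- The number 30 does not rest on the within-person comparison. The protocol cites a pilot and homogeneity.
- The protocol does not say that withdrawn participants' data are discarded. Replacing one arm only suggests that the completed arm is kept.
- The sentence on freedom to withdraw is an ethics statement. It is not evidence of why people will leave.

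**Conclusion.** The concern holds for the one-arm route. The protocol allows an arm to be filled by a person selected for it, so that arm is not randomised, the contrast lies between two people, and sequence and period are undefined for a second-period replacement. These defects need no assumption about correlation.

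Bias toward the device is a possibility. It depends on withdrawal being related to discomfort or lack of benefit, which the protocol cannot show.

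The precision loss runs from about 2 to about 34 percentage points of power (78% to 46%, against 80%) for three two-person pairs over ρ = 0.5 to 0.95. This rests on the assumed 80% starting power, ρₘ = 0.3 and an ordinary paired analysis of levels. It would be tempting to say that the trial loses nearly half its power, but that needs ρ = 0.95, and nothing in the protocol fixes that value.

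**What to change.** Amend the Analysis section as follows.

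1. Delete the one-arm, matched replacement option in both places: under matching and sampling strategies, and in the answer on withdrawal.
2. State that any added participant enters by fresh randomisation to a two-period sequence, and not by matching.
3. State that all data from every randomised participant are kept in the allocated sequence. Analyse them in a mixed model with treatment, period and a random participant effect, so that people with one period still contribute.
4. Report withdrawals by period and treatment.

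Replacement by someone who does both periods need not be banned, provided items 2 and 3 apply.

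**Cost.** If withdrawn participants are not replaced, only wording changes; the price is slight imbalance and fewer complete pairs (76% power with 27 complete pairs on the assumptions above, before any gain from one-period data). If they are replaced, each addition is a full two-period participant: 17 appointments, two of them phone calls, and the stated funding of $11,870.55 per participant.
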